3.2.10 Eastern Cooperative Oncology Group (ECOG) Performance Status (PS) of 0-1

3.2.11 Prior neoadjuvant chemotherapy is allowed

3.2.12 Patients must have fully recovered from all effects of surgery. Patients must have had at least two weeks after minor surgery and four weeks after major surgery before starting therapy. Minor procedures requiring "Twilight" sedation such as endoscopies or

mediport placement may only require a 24-hour waiting period, but this must be discussed with an investigator.

3.2.13 Women of childbearing potential must have a negative serum pregnancy test within 14 days prior to initiation of treatment and/or postmenopausal women must be amenorrheic for at least 12 months to be considered of non-childbearing potential

3.2.14 Patient is capable of understanding and complying with parameters as outlined in the protocol and able to sign and date the informed consent, approved by the Institutional Review Board (IRB), prior to the initiation of any screening or study-specific procedures

Table 1. ECOG Performance Status

Grade	ECOG
0	Fully Active, able to carry on all pre-disease performance without restriction.
1	Restricted in physically strenuous activity but ambulatory and able to carry out work of a light or sedentary nature, e.g., light housework, office work.
2	Ambulatory and capable of all self-care but unable to carry out any work activities. Up and about more than 50% of waking hours.
3	Capable of only limited self care, confined to bed or chair more than 50% of waking hours.
4	Completely disabled. Cannot carry on any self-care. Totally confined to bed or chair.

3.3 Exclusion Criteria

3.3.1 Ampullary adenocarcinoma

3.3.2 Women who are pregnant or breastfeeding

3.3.3 Macroscopic positive margins (R2) or evidence of residual local or metastatic disease

3.3.4 Resection not including pancreaticoduodenectomy

3.3.5 Known allergy or intolerance to leucovorin, 5-fluorouracil, oxaliplatin, or irinotecan

3.3.6 Prior radiation to the upper abdomen

3.3.7 Inability to swallow pills or bowel obstruction

3.3.8 Any invasive cancer in the previous 3 years requiring chemotherapy, radiation, or anticancer therapy following surgery

3.3.9 Insurance unwilling to pre-authorize PRT, FFX, and (if necessary) pegfilgrastim

3.3.10 Clinically significant liver disease

3.3.10.1 Patients with resolved hepatitis B infection are eligible if HBsAg testing is negative

3.3.10.2 Patients with resolved hepatitis C infection are eligible if viral RNA PCR is negative

3.3.11 Uncontrolled HIV infection (CD4 count must be at least 200 and viral load undetectable on a stable antiretroviral regimen to be eligible for enrollment)

3.3.12 Major surgery within 4 weeks prior to enrollment

3.4 Prior and Concomitant Therapy

Any medication or vaccine (including over-the-counter or prescription medicines, vitamins and/or herbal supplements) that the subject is receiving at Screening up to the Final Visit must be recorded in source documents and the case report forms (CRFs). The reason for use, date(s) of administration (including start and end dates), and dosage information (including dose and frequency) must be recorded. Any change in concomitant therapy during the study period must be similarly recorded. Questions regarding prior or concomitant therapy should be directed to one of the investigators.

3.4.1 Prior Anti-Cancer Therapy

For purposes of this protocol, anti-tumor treatment may be defined as, but is not limited to, anti-cancer agents (cytotoxic chemotherapy, immunotherapy, or biologic therapy), radiotherapy, and investigational agents. An investigational agent is any drug or therapy not currently approved for use in humans. No anti-cancer therapy is allowed while patients are on trial except for FFX and PRT. Prior neoadjuvant chemotherapy is allowed, but prior radiation to the upper abdomen is not.

3.4.2 Prior Surgery

Patients must have fully recovered from all effects of surgery. Patients must have had at least two weeks after minor surgery and four weeks after major surgery before starting therapy. Minor procedures requiring “Twilight” sedation such as endoscopies or mediport placement may only require a 24 hour waiting period, but this must be discussed with an investigator.

3.4.3 Supportive Care

Subjects should receive best supportive care and treatment of symptoms during the study as appropriate, including transfusion of blood and blood products, oxygen therapy, nutritional support, intravenous fluids, and treatment with appropriate medications (antibiotics, antiemetics, antidiarrheals, and analgesics, etc.). Medications, including steroids, which are given for supportive care, such as appetite stimulation, may be given concurrently.

3.4.3.1 Bisphosphonates and denosumab

Bisphosphonates and denosumab are permitted for the treatment of osteoporosis. Chronic concomitant bisphosphonate/denosumab therapy for the prevention of bone metastasis is not permitted.

3.4.3.2 Hematopoietic growth factors

Hematopoietic growth factors may be used according to ASCO guidelines. Pegfilgrastim is recommended as outlined in Section 5.0.

4.0 TRIAL DESIGN AND DETAILED STUDY PROCEDURES

4.1 Treatment Plan Overview

[figure not shown]
The study is a phase I, single-arm study to establish safety and feasibility of proton-based radiation therapy integrated within adjuvant FFX for patients with resected PDAC. Patients who have completed 2 cycles of FFX for resected pancreatic adenocarcinoma of the head of the pancreas will be eligible for enrollment. PRT will occur between cycles 6 and 7.

In dose level 1 (DL1), patients will complete cycle 6 chemotherapy (days 1-3) and then receive 5 days of daily 5 GyE proton therapy on days 15-19 (excluding weekend days) in a 28 day cycle, prior to starting cycle 7 (see Figure 1). In DL2, patients will complete cycle 6 chemotherapy (days 1-3) and then receive 5 days of daily 5 GyE proton therapy on days 8-12 (excluding weekend days) in a 21 day cycle, prior to starting cycle 7. A 3+3 dose-escalation schema will be used, requiring 3-12 patients to be enrolled.

Using a 3+3 dose-escalation design, if 0 of 3 patients experience a dose-limiting toxicity (DLT) at DL1, then 3 patients will then be enrolled in DL2. If 1 of 3 patients experiences a DLT at DL1, then 3 additional patients will be enrolled at DL1. If 2-3 of 3 patients experience a DLT at DL1, then the study is terminated. If 1 of 6 patients experiences a DLT at DL1, then 3 patients will be enrolled at DL2. If 0-1 of 3 patients experiences a DLT at DL2, then 3 additional patients will be enrolled at DL2. If 2-3 patients experience a DLT at DL2, treatment will continue at DL1 until 6 patients are enrolled at DL1. If 0-1 of 6 patients experiences a DLT at DL2, then DL2 is the recommended phase 2 dose and schedule (RP2D). Conversely, if 0-1 of 6 patients experiences a DLT at DL1 AND 2 or greater patients experience a DLT at DL2, then DL1 is the RP2D. All cycles will be 14 days, except cycle 6 which is extended to 28 days in DL1, including the 5 daily doses of PRT on days 15-19 (excluding weekend days), and 21 days in DL2, including the 5 daily doses of PRT on days 8-12 (excluding weekend days, see Figure 1 below).

If a scheduled PRT dose falls on a weekend or holiday, then the next daily dose falls on the next business day. The 5 daily doses should be completed in the shortest possible time interval (e.g. 7 days total if 2 are weekend days).

Figure 1. Study Schema
Cycles 1-5, 8-12 (14 days)

4.2 Detailed Study Plan

4.2.1 Screening

Study activities are detailed in Tables 2 (DL1) and 3 (DL2), and a study activity checklist in Table 4. Screening will occur within 28 days prior to Cycle 6 Day 1 of FFX. Signed informed consent will be obtained from the subject or the subject's legally acceptable representative before any study-specific procedures are undertaken. For procedures performed at screening and repeated, the later procedure performed prior to dosing, will serve as a baseline for clinical assessment. A complete history and physical will be obtained at the screening visit. Additionally, labs will be reviewed/ordered during the screening visit, prior to the initiation of therapy.

Patients who pass screening will undergo PRT planning and a full evaluation on Cycle 6 Day 1, including a physical examination, vital signs, performance status, chemistry, hematology, medication review, and adverse event evaluation. If any abnormality is identified at subject assessment on Cycle 6 Day 1, the patient will be deemed a screen failure and will not start treatment.

All patients who start study treatment on cycle 6 day 1 will be eligible for the primary safety analysis. We will substitute patients who screen fail or screen and do not begin study treatment as above.

The screening procedures include the following listed below.

4.2.1.1 Informed Consent

Signed informed consent will be obtained from the subject or the subject's legally acceptable representative before any study-specific procedures are undertaken.

4.2.1.2 Medical History

The following information will be collected during the Screening Period:

- 1) Complete medical history, including documentation of any clinically significant medical conditions
- 2) History of tobacco and alcohol use
- 3) Presence and severity of any symptoms/conditions associated with metastatic pancreatic cancer
- 4) Detailed oncology history, including:
 - a. Date of primary cancer diagnosis
 - b. Pathology (histology or cytology) of primary tumor
 - c. Surgical history
 - d. Anti-cancer treatments administered (including dates and type of modality)
- 5) At each visit, the subject's medical history will be reviewed and any changes from baseline will be recorded in the case report form (CRF). On C6D1, any changes observed from the screening assessments, prior to dosing, will be recorded in the subject's medical history. All medications (prescription or over-the-counter, including vitamins and/or herbal supplements) will be recorded beginning with the screening visit and continuing up through the date of the off study visit.

4.2.1.3 Demographics

Age, gender, race and ethnicity will be recorded.

4.2.1.4 Review subject eligibility criteria

4.2.1.5 Review previous and concomitant medications

4.2.1.6 Physical exam including vital signs, height, and weight

A complete physical examination will be performed at the screening visit. Body weight will be recorded during every physical exam. The subject will wear lightweight clothing and no shoes during weighing. Height will be measured at the screening visit only; the subject will not wear shoes.

4.2.1.7 Vital sign determinations

Vital sign determinations of heart rate, blood pressure and body temperature will be obtained at the screening visit. If possible, blood pressure and heart rate measurements should not immediately follow scheduled blood collections.

4.2.1.8 Performance Status

Performance status will be evaluated prior to study entry according to Table 1.

4.2.1.9 Hematology

Hematology samples (CBC with differential) will be collected and assessed using a certified laboratory. The Investigator will review, initial and date all laboratory results. Any laboratory value outside the reference range stated in the inclusion criteria will preclude the patient from study participation.

4.2.1.10 Serum chemistries

Comprehensive metabolic panel (CMP) to include: albumin, alkaline phosphatase, ALT, AST, BUN, creatinine, electrolytes (sodium, potassium, calcium, chloride, bicarbonate), glucose, and total bilirubin. Any laboratory value outside the reference range stated in the inclusion criteria will preclude the patient from study participation.

4.2.1.11 Pregnancy Test

For female subjects of childbearing potential, a serum pregnancy test will be performed at the screening visit within 28 days of C6D1 and a urine pregnancy test will be done at the C6D1 visit prior to the first dose of study drug. Subjects considered not of childbearing potential must be documented as being surgically sterile or post-menopausal (for at least 1 year). The test results must be reviewed and determined to be negative prior to dosing. If the urine pregnancy test is positive at C6D1, it should be confirmed by a serum pregnancy test. The test may be repeated at the discretion of the investigator at any time during the study. Should a female study subject become pregnant or suspect she is pregnant while participating in this study, she should inform the treating Investigator immediately.

4.2.1.12 Tumor assessment

Only patients with no evidence of local recurrence or metastatic disease will be eligible to enter onto the study. Patients with suspected disease recurrence will have to be evaluated to rule out disease recurrence prior to study enrollment.

4.3 Patient Study Number Assignment and Sample Labeling

4.3.1.1 Patient Study Number Assignment

Patients will be de-identified and assigned with a 3-digit study label (XXX).

4.4 Detailed Patient Assessments

Subject assessments (physical examinations, vital signs, performance status, chemistry, hematology, medication review, and adverse event evaluations) will be conducted at screening, C6D1, C6D15 (DL1) or C6D8 (DL2), and D1 of every subsequent cycle (every 14 days \pm 3 days). Details are provided in Tables 2 and 3, and a checklist highlighting the important events for screening through the completion of the trial is provided below in Table 4. Patients will meet with the radiation oncologist during screening (prior to C6D1), during PRT, and at follow-up visits as outlined below.

4.4.1 Physical Examinations

A complete physical examination will be performed at the screening visit, on C6D1, C6D15 (DL1) or C6D8 (DL2), and D1 of every subsequent cycle (every 14 days \pm 3 days). Any significant physical examination findings after the administration of the first doses PRT will be recorded as adverse events. Body weight will be recorded during every physical exam. The subject will wear lightweight clothing and no shoes during weighing. Weight will be measured on the same scale at each visit. Height will be measured at the screening visit and C6D1 only; the subject will not wear shoes.

4.4.2 Medical History

At each visit, the subject's medical history will be reviewed and any changes from baseline will be recorded as an adverse event. On C6D1, any changes observed from the screening assessments, prior to dosing, will be recorded in the subject's medical history. All medications (prescription or over-the-counter, including vitamins and/or herbal supplements) will be recorded beginning with the screening visit and continuing up through the date of the final visit.

4.4.3 Vital Signs

Vital sign determinations of body temperature (in degrees Celsius), heart rate, respiratory rate, blood pressure and pain (using a 0-10 Numeric Ranking Scale) will be obtained at the screening visit, on each day the subject is seen by the treating physician, and at the final visit. If possible, blood pressure and heart rate measurements should not immediately follow scheduled blood collections.

4.4.4 Clinical Laboratory Tests

All subjects will undergo the laboratory assessments outlined in Tables 2 and 3.

- 1) A complete blood count (CBC) with differential will be collected at the screening visit, on C6D1, C6D15 (DL1) or C6D8 (DL2), and D1 of every subsequent cycle (every 14 days \pm 3 days).
- 2) Serum chemistries (total protein, albumin, total bilirubin, AST, ALT, alkaline phosphatase, sodium, potassium, chloride, bicarbonate, BUN, creatinine, and calcium) will be collected at the screening visit, on C6D1, C6D15 (DL1) or C6D8 (DL2), and D1 of every subsequent cycle (every 14 days \pm 3 days).
- 3) PT/INR and aPTT will be collected at the screening visit (this may be repeated during the course of the study at the discretion of the investigator but is not required).

Laboratory samples for this study will be assessed using the certified laboratory at the investigators' institutions, or at a clinical laboratory such as Quest or LabCorp and these data will be used for all data analysis. The Principal Investigator or sub-investigator will review, initial and date all laboratory results. Any laboratory value outside the reference range that is considered clinically significant by the investigator will be followed as appropriate. Clinically significant laboratory values will be recorded as adverse events if they meet the criteria as specified in Section 6.0.

4.4.5 Adverse Event Evaluation

The Principal Investigator or sub-investigators will assess adverse events, laboratory data and vital signs throughout the study. Adverse events will be assessed by NCI CTCAE Version 5.0. https://ctep.cancer.gov/protocoldevelopment/electronic_applications/docs/CTCAE_v5_Quick_Reference_5x7.pdf. The investigators will monitor each subject for clinical and laboratory evidence of adverse events on a routine basis throughout the study. The investigator will assess and record any adverse event in detail including the date of onset, event diagnosis (if known) or sign/symptom, severity, time course, duration and outcome, relationship of the adverse event to study drug, and any action(s) taken. For serious adverse events not considered "probably related" to study drug, the investigator will provide an "Other" cause of the event. For adverse events to be considered intermittent, the events must be of similar nature and severity. Adverse events, whether in response to a query, observed by site personnel, or reported spontaneously by the subject will be recorded. All adverse events will be followed to a satisfactory conclusion.

4.4.6 Imaging and Evaluation

Patients will undergo a baseline tumor evaluation with imaging studies within 28 days prior to C6D1. Imaging studies should include a diagnostic CT scan of the chest, abdomen, and pelvis with PO and IV contrast (unless medically contraindicated). If a patient has an allergy to IV contrast, appropriate pre-medication can be given to prevent a contrast reaction. Patients may undergo other modalities such as an MRI instead of a CT scan at the treating physician's discretion if appropriate (such as severe allergy to CT contrast, extremity tumors, bone metastases requiring bone scans, etc.).

The first follow-up surveillance scan will occur within 14 days of the End of Treatment (EOT) visit which will be scheduled following completion of C12 or the last cycle of FFX administered. Follow-up visits including scans (CT or MRI) and blood work including CA19-9 will then occur every 3 months up to 24 months.

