4.4.8 Protocol Deviations

The investigator should not implement any deviation from the protocol without prior review and agreement by the Sponsor and in accordance with the IRB and local regulations, except when necessary to eliminate an immediate hazard to study subjects.

Table 2. Study Activities – Dose Level 1

	Screening ^a	C6D1 ^b	C6D2	C6D3	C6D15	C6D16	C6D17	C6D18	C6D19	D1 of C7 ^c -C12	EOT ^d	F/U ^e
Informed Consent	X											
Demographics	X											
Medical History	X											
ECOG PS ^f	X	X			X					X	X	X
Concomitant Medications Collection	X	X			X					X	X	X
Adverse Events Assessment	X	X			X					X	X	X
Vital Signs	X	X			X					X	X	X
Height	X	X										
Weight	X	X			X					X	X	X
History and Physical Exam	X	X			X					X	X	X
CT or MRI Scan Tumor Evaluation and Assessment ^g	X										X ^h	X
β-hCG ⁱ	X	X										
CBC with differential	X	X			X					X	X	X
CMP ^j	X	X			X					X	X	X
PT/INR and aPTT	X											
CA19-9	X	X								X	X	X
mFOLFIRINOX		X	X	X						X		
Proton Beam Planning	X											
Proton Beam Therapy					X	X	X	X	X			
Survival		X			X					X	X	X

^aScreening visit must occur within 28 days of C6D1 of mFOLFIRINOX

^bThis assumes proton therapy will be administered during C6 (may be delivered during C6-C11 if necessary)

^cC6 is a 28 day cycle in dose level 1 (C7D1 = C6D29), all other cycles are 14 days in length

^dEnd of treatment (D1 of last cycle of mFOLFIRINOX, typically C12)

^eFollow-up assessments will be performed every 3 months for up to 24 months

^fEastern Cooperative Oncology Group Performance Status

^gScreening scans should be done within 2 months of C6D1

^hCan be performed within 14 days of the EOT visit

ⁱSerum (screening) and urine (C6D1) pregnancy tests (for women of childbearing potential only)

^jComprehensive metabolic panel: sodium, potassium, chloride, bicarbonate, BUN, creatinine, glucose, calcium, AST, ALT, alkaline phosphatase, total bilirubin, total protein, and albumin

Table 3. Study Activities – Dose Level 2

	Screening ^a	C6D1 ^b	C6D2	C6D3	C6D8	C6D9	C6D10	C6D11	C6D12	D1 of C7 ^c -C12	EOT ^d	F/U ^e
Informed Consent	X											
Demographics	X											
Medical History	X											
ECOG PS ^f	X	X			X					X	X	X
Concomitant Medications Collection	X	X			X					X	X	X
Adverse Events Assessment	X	X			X					X	X	X
Vital Signs	X	X			X					X	X	X
Height	X	X										
Weight	X	X			X					X	X	X
History and Physical Exam	X	X			X					X	X	X
CT or MRI Scan Tumor Evaluation and Assessment ^g	X										X ^h	X
β-hCG ⁱ	X	X										

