7.0 EFFICACY ASSESSMENT

7.1 Efficacy Variables

Disease recurrence will be assessed by a CT scan (or other appropriate modalities such as by way of MRI consistent with the modality used prior to treatment) utilizing RECIST v1.1 criteria. Assessments will be performed within 2 months of C6D1, at EOT, and at follow-up visits.

We will track the success rate in screening patients, completion of PRT planning, completion of proton beam treatment, and completion of adjuvant therapy (including number of cycles completed and relative dose intensity).

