7.2.1.3 Non-measurable Lesions

All other lesions, including small lesions (longest diameter < 20 mm with conventional techniques or < 10 mm with a CT scan), bone lesions, leptomeningeal disease, ascites, pleural/pericardial effusion, inflammatory breast disease, lymphangitis cutis/pulmonis, cystic lesions and also abdominal masses that are suspicious though may or may not be confirmed and followed by imaging techniques.

All measurements should be taken and recorded in metric notation, using a ruler or calipers. All baseline evaluations should be performed as closely as possible to the beginning of treatment and never more than 14 days before the beginning of the treatment. The same method of assessment and the same technique should be used to characterize each identified and reported lesion at baseline and during follow-up. Clinical lesions will only be considered measurable when they are superficial (e.g., skin nodules and palpable lymph nodes). For the case of skin lesions, documentation by color photography including a ruler to estimate the size of the lesion is required.

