7.3 Definition of Disease Recurrence

Disease progression will be defined as:

- 1) Radiologic progression of disease by RECIST v1.1 criteria.
- 2) Clinical progression as determined by the investigator, which may be characterized as, but is not limited to:
 - a. Increase of at least 2 points in ECOG performance status attributable to cancer progression.
 - b. Requirement for radiation (beyond palliative radiation for bone pain relief as outlined in 3.4.3.3), chemotherapy or surgery.
- 3) Death from disease progression

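### The baseline scan window is 28 days in one section and 2 months in others, and item 2b of the recurrence definition is not tied to cancer

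*Combined protocol and SAP*

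**What the plan says.** **Baseline scan.** Section 4.2.1.12 makes freedom from disease a condition of entry: "Only patients with no evidence of local recurrence or metastatic disease will be eligible to enter onto the study". The age allowed for the scan that shows this differs by place:

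- Section 4.4.6: "Patients will undergo a baseline tumor evaluation with imaging studies within 28 days prior to C6D1".
- Section 7.1: "Assessments will be performed within 2 months of C6D1, at EOT, and at follow-up visits". Footnote g of Tables 2 and 3 gives the same 2 months for screening scans.
- Section 7.2.1.3, in general RECIST text on measuring lesions: baseline evaluations are to be "never more than 14 days before the beginning of the treatment".

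The scan row of Tables 2 and 3 is marked at screening, EOT and follow-up, with nothing between screening and EOT.

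**Recurrence definition.** Section 7.3 is headed as a definition of recurrence but defines progression. Its second criterion is clinical progression as judged by the investigator, with an open-ended list of examples. Item 2a is a fall in ECOG status that must be due to the cancer. Item 2b reads: "Requirement for radiation (beyond palliative radiation for bone pain relief as outlined in 3.4.3.3), chemotherapy or surgery". RFS (8.4.1) runs from surgery to evidence of recurrence, and 7.3 is the only definition of that event.

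**Checklist.** Section 4.4 says that "a checklist highlighting the important events for screening through the completion of the trial is provided below in Table 4". The screening block of Table 4 lists the scan and the tumor assessment. The EOT and follow-up blocks list neither.

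**The concern.** The same scan can be compliant under one section and a deviation under another, and nothing says which section governs. Because the scan supports an entry condition, this is an eligibility question as well as an endpoint question. An older scan leaves more time for an undetected recurrence before proton therapy, and such a patient would later enter the RFS analysis.

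Item 2b has a different problem. Every patient is on protocol chemotherapy and is due to receive protocol radiation, and some will need treatment changes or procedures because of toxicity. Gastrointestinal obstruction of grade 3 or more is itself a listed DLT in 6.9. Item 2b lacks the attribution to cancer that 2a has, so an operation for obstruction, or a change of regimen for intolerance, could be recorded as recurrence. Its one exception, for palliative bone radiation, points to a section 3.4.3.3 that does not exist; 3.4.3 ends at 3.4.3.2.

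**Working it through.** The plan gives no figure of its own on this point, so there is none to reproduce. The check compares the passages and then sizes the effect under stated assumptions.

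**1. The windows side by side.** Section 4.2.1 refers to "All patients who start study treatment on cycle 6 day 1", so C6D1 is taken as the start of treatment for the 14-day sentence.

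| Scan age at C6D1 | 4.4.6 (28 days) | 7.1 and footnote g (2 months) | 7.2.1.3 (14 days) |
|---|---|---|---|
| 10 days | meets | meets | meets |
| 20 days | meets | meets | fails |
| 40 days | fails | meets | fails |

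**2. Position on the cycle calendar.** Footnote c of Tables 2 and 3 says that, apart from cycle 6, "all other cycles are 14 days in length". Without delays, C1D1 to C6D1 is 5 × 14 = 70 days. The 28-day limit reaches back to C4D1. Two months (59 to 62 days) reaches back to days 9 to 12 of cycle 1. Two cycles are complete 70 − 28 = 42 days before C6D1, so the longer window admits a scan taken before the patient had the two cycles required for eligibility.

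**3. Chance of recurrence between scan and C6D1.** Assumptions: constant hazard, and median RFS m of 12 to 20 months (not given in the documents). For a scan d days old, P = 1 − 0.5^(d/(30.44 × m)).

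| d | m = 20 | m = 12 | Expected of 12 patients |
|---|---|---|---|
| 14 | 1.6% | 2.6% | 0.2-0.3 |
| 28 | 3.1% | 5.2% | 0.4-0.6 |
| 61 | 6.7% | 10.9% | 0.8-1.3 |

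The last column supposes that all 12 scans are exactly d days old. If ages were spread evenly from 0 to d, the values would be about half. No allowance is made for recurrences caught clinically or by CA19-9.

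**4. Interval without imaging, dose level 1.** C6D1 to C12D1 is 28 + 5 × 14 = 98 days. Footnote d places EOT on day 1 of the last cycle, and the EOT scan may follow within 14 days.

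- 61-day-old baseline: 61 + 98 + 14 = 173 days.
- 28-day-old baseline: 28 + 98 + 14 = 140 days.

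The difference is 33 days; the other 98 + 14 = 112 days arise whichever window applies. Section 4.4.6 schedules EOT after cycle 12 is complete, which adds 14 days (187 instead of 173). Cycle delays would add more, so 173 is not a maximum.

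**5. Effect of item 2b on median RFS.** Assumption: a share f of patients has a toxicity-driven event scored as recurrence before the resulting median, independently of true recurrence. Then the median solves (1 − f) × exp(−λt) = 0.5 with λ = ln 2/20, so t = ln(2(1 − f))/λ.

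- f = 0.10: ln 1.8/0.03466 = 17.0 months.
- f = 0.20: ln 1.6/0.03466 = 13.6 months.

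Both compare with a true median of 20 months. The documents give no value for f.

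**The case against.** Several points on the other side are sound.

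- The 14-day sentence is general RECIST wording about measuring lesions and does not name C6D1. Patients with residual disease are excluded, so there should be no lesions to measure at baseline. The firm conflict is between 28 days and 2 months.
- Footnote g could be read as a deliberate exception to the 28-day screening window in footnote a. That would settle the tables, but not 4.4.6, which sets 28 days for imaging specifically.
- A reader might infer that an old scan simply lets recurred patients in. The documents do not support that. Section 4.2.1.12 requires suspected recurrence to be ruled out before enrollment, CA19-9 is drawn at screening and C6D1, and 4.2.1 makes any abnormality at the C6D1 assessment a screen failure. These are partial safeguards; none is a repeat scan.
- A reader might infer that item 2b automatically turns toxicity into recurrence. It does not. The investigator must first judge that the disease has progressed, and 2b is only an example. A misclassification is possible, not certain.
- Item 2b is not the only route to withdrawal. Section 4.4.10.1 already withdraws anyone needing other radiotherapy or alternate antineoplastic agents, and 4.4.10.2 requires a final visit with tumor assessment and a recorded reason. What 2b adds is the possible recurrence label.
- A reader of Table 4 might infer that no scans are planned at EOT or follow-up. Sections 4.4.6 and 7.1 and Tables 2 and 3 all require them. The gap is a checklist omission, and any lost scans would be a matter of site conduct that the documents do not establish.

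What remains is the conflict over the baseline window and the missing attribution in item 2b.

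**Conclusion.** The concern holds in two parts. First, the window for the scan confirming freedom from recurrence is 28 days in 4.4.6 and 2 months in 7.1 and footnote g, with a weaker third conflict from 7.2.1.3. The documents do not show which governs. Second, 7.3 item 2b is over-broad, because a toxicity-driven treatment change or operation could be scored as an RFS event.

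The size is modest. Moving from the oldest permitted scan to a 28-day limit would lower the expected number of recurrences between scan and C6D1 from 0.8-1.3 to 0.4-0.6 of 12 patients. That assumes medians of 12 to 20 months and every scan at its limit. The shift in median RFS depends wholly on an assumed misclassification rate and shows direction and scale only.

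RFS is exploratory, described by Kaplan-Meier in at most 12 patients, and no decision rule uses it. It would be wrong to conclude that the primary endpoint is compromised: DLTs are scored from their own list over their own 28-day window, and neither they nor the RP2D depend on 7.3.

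**What to change.** 1. State one baseline imaging window in 4.4.6, 7.1, footnote g of Tables 2 and 3, and 7.2.1.3. Twenty-eight days would match the protocol's own screening window. The cost is a repeat scan before C6D1 for some patients whose scan is older.
2. In 7.3, define recurrence instead of progression. Count new radiation, chemotherapy or surgery only when given for documented recurrence, and date the event at first detection. Remove or correct the reference to 3.4.3.3. This is a wording change.
3. Add the CT/MRI and tumor assessment lines to the EOT and follow-up blocks of Table 4. This is a clerical alignment and adds no scans, since Tables 2 and 3 already require them.
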